3.4.3.4 Corticosteroids

Chronic dosing of corticosteroids such as dexamethasone and prednisone is known to lead to induction of CYP3A enzymes, thereby potentially increasing the risk of reducing LEE011 drug exposure to subtherapeutic levels. Systemic corticosteroid treatment should not be given during the study, except for:

- Topical applications (e.g., rash), inhaled sprays (e.g., obstructive airways diseases), eye drops or local injections (e.g., intra-articular);

A short duration (< 5 days) of systemic corticosteroids \leq to the anti-inflammatory potency of 4 mg dexamethasone (e.g. for chronic obstructive pulmonary disease, or as an antiemetic)

3.4.4 Drugs with QT prolongation

As far as possible, avoid co-administration of QT prolonging drugs or any other drugs with the potential to increase the risk of drug-related QT prolongation (e.g., via a potential DDI that increases the exposure of LEE011 or the exposure of the QT prolonging drug). A definitive list of drugs with a known risk, possible risk, or conditional risk of QT prolongation and/or Torsades de Pointes (TdP) is available online at www.qtdrug.org.

Medications with a known risk for QT prolongation are prohibited during study treatment.

3.4.5 Permitted concomitant therapy requiring caution

Medications to be used with caution during LEE011 and everolimus in this study are listed below (see Table 3). This list is not comprehensive and is only meant to be used as a guide. These medications should be excluded from patient use if possible. If they must be given, then use with caution and consider a LEE011 and everolimus interruption if the concomitant medication is only needed for a short time.

- Moderate inhibitors or inducers of CYP3A4/5
- Sensitive substrates of CYP3A4/5 that do not have narrow therapeutic index
- Strong inhibitors of BSEP
- Sensitive substrates of the renal transporters, MATE1 and OCT2
- Sensitive substrates of BCRP
- Medications that carry a possible risk for QT prolongation

Table 5. List of Medications to be Used with Caution During Study Drug Treatment

Category	Drug Name
Moderate CYP3A4/5 inhibitors	Aprepitant, amprenavir, asafoetida resin (Ferula asafoetida) cimetidine, crizotinib, diltiazem, faldaprevir, imatinib, isavuconazole, netupitant, nilotinib, tofisopam, Schisandra sphenanthera (nan wu wei zi), verapamil
Moderate CYP3A4/5 inducers	Bosentan, dabrafenib, efavirenz, etravirine, genistein, lopinavir ⁵ , modafinil, nafcillin, telotristat
Sensitive CYP3A4/5 substrates ¹	Alpha-dihydroergocryptine, aprepitant, atorvastatin, avanafil, bosutinib, brotizolam, budesonide, buspirone, cobimetinib, darifenacin, dasatinib, ebastine, eletriptan, eplerenone, everolimus, felodipine, fluticasone, grazoprevir, ibrutinib, isavuconazole, ivabradine, ivacaftor, , levomethadyl (LAAM), lomitapide, lovastatin, lumefantrine, lurasidone, maraviroc, midazolam, midostaurin, naloxegol, neratinib, nisoldipine, perospirone, quetiapine, ridaforolimus, sildenafil, simeprevir, simvastatin, ticagrelor, tilidine, tolcapten, triazolam, ulipristal, vardenafil, venetoclax, vicriviroc, voclosporin
BSEP inhibitors	Alectinib, atorvastatin, bromocriptine, candesartan, clobetasol, clofazimine, dabigatran, dipyrindamole, glyburide, grazoprevir, ledipasvir, mifepristone, pioglitazone, reserpine, rifamycin, simeprevir, telmisartan, timcodar, troglitazone, valinomycin, velpatasvir
Medications that carry a possible risk for QT prolongation ²	Alfuzosin, apomorphine, aripiprazole, artemisinol+piperaquine, asenapine, atomoxetine, bedaquiline, bendamustine, bortezomib, bosutinib, buprenorphine, cabozantinib, capecitabine, ceritinib, clomipramine, crizotinib, clozapine, cyamemazine (cyamempromazine), dabrafenib, dasatinib, degarilix, delamanid, desipramine, dexmedetomidine, dolasetron, efavirenz, eliglustat, epirubicin, eribulin mesylate, ezogabine (retigabine), famotidine, felbamate, fingolimod, flupentixol, gemifloxacin, granisetron, hydrocodone-ER, iloperidone, imipramine (melipramine), isradipine, ketanserin, lapatinib, lenvatinib, leuprolide, lithium, melperone, midostaurin, mifepristone, mirabegron, mirtazapine, moexipril/HCTZ, necitumumab, nicardipine, nilotinib, norfloxacin, nortriptyline, nusinersen, ofloxacin, osimertinib, oxytocin, paliperidone, palonosetron, panabinostat, pasireotide, pazopanib, perflutren lipid microspheres, perphenazine, pilsicainide, pimavanserin, pipamperone, promethazine, prothipendyl, rilpivirine, risperidone, romidepsin, sertindole, sorafenib, sunitinib, tamoxifen, tipiracil/trifluridine, tizanidine, tolterodine, toremifene, trimipramine, tropisetron, vardenafil, vemurafenib, venlafaxine, vorinostat, ziprasidone
MATE1/2 substrates ³	Acyclovir, cephalixin, cimetidine, fexofenadine, ganciclovir, glycopyrronium, metformin, pindolol, pilsicainide, ranitidine, topotecan, varenicline
OCT1/2 substrates ⁴	Amantadine, 6-beta-hydroxycortisol, carboplatin, cisplatin, cephalixin, cephradine, ipratropium, lamivudine, linagliptin, metformin, oxyplatin, oxybutynin, phenformin, picoplatin, pilsicainide, pindolol, ranitidine, sorafenib, tropisetron, trospium, umecidine, and zidovudine
BCRP substrates	Daunorubicin, dolutegravir, doxorubicin, hematoporphyrin, imatinib, methotrexate, mitoxantrone, pitavastatin, rosuvastatin, irinotecan, ethinyl estradiol, simvastatin, sulfasalazine, sofosbuvir, tenofovir, topotecan, venetoclax
¹ Sensitive substrates: Drugs whose plasma AUC values have been shown to increase 5-fold or higher when co-administered with a potent inhibitor. ² The list provided is as of January 2018. Check https://www.crediblemeds.org/healthcare-providers/drug-list for the most updated list. ³ MATE1 and MATE2 share considerable substrate specificity. ⁴ OCT1 and OCT2 share considerable substrate specificity. ⁵ Lopinavir is prohibited when combined with ritonavir Source: Novartis PK Sciences Memorandum: Drug-Drug Interactions (DDI) and Co-medication Considerations for Novartis Clinical Trials (January 2018), which is compiled from Indiana University "Clinically Relevant" Flockhart Table™, University of Washington Drug Interaction Database, and FDA Drug Development and Drug Interactions: Table of Substrates, Inhibitors and Inducers.	

3.4.6 Prohibited concomitant therapy

The following medications are prohibited during study treatment in the study (see Table 4). This list is not comprehensive and is only meant to be used as a guide.

- Strong inhibitors or inducers of CYP3A4/5
- Substrates of CYP3A4/5 with a narrow therapeutic index

- Medications that carry a known risk for QT prolongation
- Other investigational and antineoplastic therapies not part of the study
- Herbal medications/preparations, dietary supplements (except for vitamins) including, but not limited to: St. John's wort, Kava, ephedra (ma huang), ginkgo biloba, dehydroepiandrosterone (DHEA), yohimbe, saw palmetto, black cohosh and ginseng. Patients should stop using all herbal medications and dietary supplements at least 7 days prior to first dose of study treatment.

Table 6. List of Prohibited Medications During Study Drug Treatment

Category	Drug Name
Strong CYP3A4/5 inhibitors	Atazanavir/ritonavir, boceprevir, clarithromycin, cobicistat, conivaptan, danoprevir/ritonavir, darunavir/ritonavir, elvitegravir/ritonavir, grapefruit juice, idelalisib, indinavir, indinavir/ritonavir, itraconazole, ketoconazole, lopinavir/ritonavir, mibefradil, nefazodone, nelfinavir, ombitasvir/paritaprevir/dasabuvir/ritonavir (VIEKIRA PAK), posaconazole, ritonavir, saquinavir/ritonavir, telaprevir, telithromycin, tipranavir/ritonavir, troleandomycin, voriconazole
Strong CYP3A4/5 inducers	carbamazepine ³ , enzalutamide, lumacaftor, mitotane, phenobarbital, phenytoin ³ , rifabutin, rifampin (rifampicin) ³ , St. John's wort (hypericum perforatum) ^{2,3}
CYP3A4/5 substrates with NTI ¹	Alfentanil, astemizole, cisapride, cyclosporine, diergotamine (dihydroergotamine), ergotamine, fentanyl, pimozide, quinidine, sirolimus, tacrolimus
Medications with a known risk for QT prolongation ⁴	Amiodarone, anagrelide, arsenic trioxide, astemizole, azithromycin, chloroquine, chlorpromazine, cilostazol, ciprofloxacin, cisapride, citalopram, clarithromycin, disopyramide, dofetilide, domperidone, donepezil, dronedarone, droperidol, erythromycin, escitalopram, flecainide, fluconazole, gatifloxacin, grepafloxacin, halofantrine, haloperidol, ibutilide, levofloxacin, levomepromazine, levosulpiride, methadone, moxifloxacin, ondansetron, oxaliplatin, papaverine HCl (intra-coronary), pentamidine, pimozide, procainamide, propofol, quinidine, roxithromycin, sevoflurane, sotalol, sulpiride, sultopride, terlipressin, terodiline, thioridazine, vandetanib
Herbal preparations/medications	Herbal preparations/medications known as strong inducers or inhibitors of CYP3A4/5 or those with a known risk of QT prolongation are prohibited throughout the study. These herbal medications include, but are not limited to: St. John's wort, Kava, ephedra (ma huang), ginkgo biloba, dehydroepiandrosterone (DHEA), yohimbe, saw palmetto, and ginseng. Patients should stop using these herbal medications 7 days prior to first dose of study drug.
Other investigational and antineoplastic therapies	Other investigational therapies must not be used while the patient is on the study. Anticancer therapy (chemotherapy, all SERMS (including raloxifene), biologic or radiation therapy, and surgery) other than the study treatments must not be given to patients while the patient is on the study medication. If such agents are required for a patient then the patient must be discontinued study drug.

¹ NTI = narrow therapeutic index drugs whose exposure-response indicates that increases in their exposure levels by the concomitant use of potent inhibitors may lead to serious safety concerns (e.g., Torsades de Pointes) or drugs which have <2-fold difference in the minimum toxic concentrations and minimum effective concentrations in the blood.

² Herbal product

³ P-gp inducer

⁴ The list provided is as of January 2018. Check <https://www.crediblemeds.org/healthcare-providers/drug-list> for the most updated list.

As far as possible, avoid co-administration of QT prolonging drugs or any other drugs with the potential to increase the risk of drug-related QT prolongation (e.g., via a potential DDI that increases the exposure of ribociclib or the exposure of the QT prolonging drug). A definitive list of drugs with a known risk, possible risk, or conditional risk of QT prolongation and/or Torsades de Pointes (TdP) is available online at qtdrugs.org.

Source: Novartis PK Sciences Memorandum: Drug-Drug Interactions (DDI) and Co-medication Considerations for Novartis Clinical Trials (January 2018), which is compiled from Indiana University "Clinically Relevant" Flockhart Table™, University of Washington Drug Interaction Database, and FDA Drug Development and Drug Interactions: Table of Substrates, Inhibitors and Inducers.

4.0 TRIAL DESIGN AND DETAILED STUDY PROCEDURES

4.1 Treatment Plan Overview

We propose a single arm, open-label Phase I/II study to evaluate the clinical activity of the combination of LEE011, a novel inhibitor of cyclin dependent kinases 4 and 6 (CDK4/6), and the mTOR inhibitor everolimus in patients with mPAC refractory to chemotherapy. We will also analyze the pharmacodynamics effects of this combination on tumor cells through serial biopsies.

4.1.1 Phase I Portion (Dose Escalation Procedures)

During the Phase I Portion of the study, patients will receive everolimus 2.5 mg once daily days 1-28 continuously and a dose of LEE011 by mouth once daily days 1-21 according to their dose level (see below):

- 3 patients are enrolled at dose level 1.
 - If 0 patients experience a DLT, 3 patients are enrolled at dose level 2.
 - If 1 patient experiences a DLT, 3 additional patients are enrolled at dose level 1. If 1 of 6 patients at dose level 1 experiences a DLT, 3 patients are enrolled at dose level 2.
 - If ≥ 2 patients experience a DLT, 3 patients are enrolled at dose level -1.
- If 0-1 of 3 patients at dose level 2 experience a DLT, then 3 additional patients are enrolled at dose level 2.
 - If 0-1 of 6 patients at dose level 2 experience a DLT, dose level 2 is the RP2D.
- If ≥ 2 of 3 patients at dose level 2 experience a DLT, 3 additional patients may be enrolled (to achieve 6 patients total) at dose level 1.
 - If 0-1 of 6 patients at dose level 1 experience a DLT, dose level 1 is the RP2D.
 - If ≥ 2 of 6 patients at dose level 1 experience a DLT, 3 patients are enrolled at dose level -1.
- If 0-1 of 3 patients at dose level -1 experience a DLT, 3 additional patients are enrolled at dose level -1.
 - If 0-1 of 6 patients at dose level -1 experience a DLT, dose level -1 is the RP2D.
 - If ≥ 2 of 3 or 6 patients at dose level -1 experience a DLT, 3 patients are enrolled at dose level -2.
- If 0-1 of 3 patients at dose level -2 experience a DLT, 3 additional patients are enrolled at dose level -2.
 - If 0-1 of 6 patients at dose level -2 experience a DLT, dose level -2 is the RP2D.
 - If ≥ 2 of 3 or 6 patients at dose level -2 experience a DLT, the study is terminated.

There will be no inpatient dose de-escalation.

4.1.2 Phase II Portion, Stage 1 – Initial Stage

The first stage of the study will be performed to establish a minimum level of clinical efficacy to warrant the enrollment of more patients in the second stage of the study. 11 patients will be enrolled and will undergo baseline imaging and a pre-treatment biopsy. The patients will then be started on treatment with at the RP2D by mouth daily for the first 21 days out of a 28 day cycle in combination with everolimus 2.5 mg by mouth daily continuously.

- LEE011 at the RP2D by mouth once daily days 1-21

- Everolimus 2.5 mg by mouth once daily days 1-28 (continuously)

Patients will be evaluated, including laboratory testing, every 2 weeks until the first restaging analysis. Restaging will occur every 8 weeks regardless of treatment cycle. If at first restaging there is no evidence of PD, as determined by RECIST v1.1 criteria, and the patient is tolerating therapy, then patients may be seen only on Day 1 of future cycles, unless clinically indicated.

Patients will have a tumor biopsy prior to treatment, a second biopsy at 2 weeks on treatment, and an optional final biopsy at the time of PD.

After all 11 patients from the initial stage have undergone their 8 week response assessment, an interim analysis will be conducted to determine how many had a PR, CR, SD, or PD. The study will be stopped early if 2 or fewer patients obtain a PR, CR, or SD at 8 weeks. If 3 or more patients obtain a PR, CR, or SD at 8 weeks, then 15 additional patients will be enrolled on the study for a total of 26 patients. Up to 3 additional patients may be screened and may be used to replace up to 3 patients in the initial 26 patients, provided those initial patients undergo screening but do not start study treatment within 3 weeks of screening. Thus, up to 29 patients may be screened for the Phase II portion of this study.

performed at screening and repeated, the later procedure performed prior to dosing, will serve as a baseline for clinical assessment. A complete history and physical will be obtained at the screening visit. Additionally, labs will be reviewed/ordered during the screening visit, prior to the initiation of therapy.

Patients who pass screening will again undergo a full evaluation on Cycle 1 Day 1, including a physical examination, vital signs, performance status, chemistry, hematology, medication review, and adverse event evaluation. If any abnormality is identified at subject assessment on Cycle 1 Day 1, prior to initiating therapy, the patient will be deemed a screen failure and will not start treatment.

For patients being considered for enrollment outside of Georgetown-Lombardi, all primary source documentation should be sent to the multi-institutional coordinator and the Study Chair, [name] for review and approval. Patients must be approved for accrual prior to starting study medications. Faxed records should be sent to [contact], with an email to the multi-institutional coordinator and [name] to confirm receipt of those records.

The screening procedures include the following listed below.

4.2.1.1 Informed Consent

Signed informed consent will be obtained from the subject or the subject's legally acceptable representative before any study-specific procedures are undertaken.

4.2.1.2 Medical History

The following information will be collected during the Screening Period:

- 1) Complete medical history, including documentation of any clinically significant medical conditions
- 2) History of tobacco and alcohol use
- 3) Presence and severity of any symptoms/conditions associated with metastatic pancreatic cancer
- 4) Detailed oncology history, including:
 - a. Date of primary cancer diagnosis
 - b. Pathology (histology or cytology) of primary tumor
 - c. Metastasis information (including the location)
 - d. Surgical history
 - e. Anti-cancer and radiation treatments administered (including dates and type of modality)
- 5) At each visit, the subject's medical history will be reviewed and any changes from baseline will be recorded in the case report form (CRF). On C1D1 any changes observed from the screening assessments, prior to dosing, will be recorded in the subject's medical history. All medications (prescription or over-the-counter, including vitamins and/or herbal supplements) will be recorded beginning with the Screening Visit and continuing up through the date of the off study visit.

4.2.1.3 Demographics

Age, gender, race and ethnicity will be recorded.

4.2.1.4 Review subject eligibility criteria

4.2.1.5 Review previous and concomitant medications

4.2.1.6 Physical exam including vital signs, height, and weight

A complete physical examination will be performed at the Screening Visit. Body weight will be recorded during every physical exam. The subject will wear lightweight clothing and no shoes during weighing. Height will be measured at the Screening Visit only; the subject will not wear shoes.

4.2.1.7 Vital sign determinations

Vital sign determinations of heart rate, blood pressure and body temperature will be obtained at the Screening Visit. If possible, blood pressure and heart rate measurements should not immediately follow scheduled blood collections.

4.2.1.8 Performance Status

Performance status will be evaluated prior to study entry according to Table 2.

4.2.1.9 Hematology

Hematology samples (CBC) will be collected and assessed using a certified laboratory. The Investigator will review, initial and date all laboratory results. Any laboratory value outside the reference range stated in the inclusion criteria will preclude the patient from study participation.

4.2.1.10 Serum chemistries

Comprehensive metabolic panel (CMP) to include: albumin, alkaline phosphatase, ALT, AST, BUN, creatinine, electrolytes (sodium, potassium, calcium, chloride, bicarbonate), glucose, total bilirubin, phosphorous, and magnesium. Any laboratory value outside the reference range stated in the inclusion criteria will preclude the patient from study participation.

4.2.1.11 Pregnancy Test

For female subjects of childbearing potential, a serum pregnancy test will be performed at the Screening Visit within 14 days of C1D1 and a urine pregnancy test will be done at the C1D1 visit prior to the first dose of study drug. Subjects considered not of childbearing potential must be documented as being surgically sterile or post-menopausal (for at least 1 year). The test results must be reviewed and determined to be negative prior to dosing. If the urine pregnancy test is positive at C1D1, it should be confirmed by a serum pregnancy test. The test may be repeated at the discretion of the investigator at any time during the study. Should a female study subject become pregnant or suspect she is pregnant while participating in this study, she should inform the treating Investigator immediately.

4.2.1.12 Tumor assessment

Only patients with metastatic pancreatic cancer not eligible for resection will be considered for entry. Subjects must have measurable disease, defined as at least 1 unidimensionally measurable lesion as defined by RECIST 1.1. Imaging for screening will be reviewed to prepare for tumor biopsies and molecular assessment.

4.3 Tumor Biopsies

Upon signing consent, patients will undergo a fresh tumor core biopsy by interventional radiologists. Tumor biopsies are mandatory UNLESS the patient has been evaluated for a biopsy in consultation with radiology in good faith, and there is a determination that an attempt at a biopsy would cause undue risk to the patient. Tumor samples will be sent to [name] at:

Roswell Park Comprehensive Cancer Center
c/o [name]
[name]
[name]

4.3.1 Patient Study Number Assignment and Sample Labeling

An additional scientific objective is to assess the pharmacodynamic effects of LEE011 and everolimus on tumor tissue and to correlate those effects to PFS. Thus, for all patients, we will require 2 core biopsies of a primary pancreatic tumor or metastatic lesion, and a third core biopsy will be optional:

- A fresh core biopsy prior to treatment (within 3 weeks of Cycle 1 Day 1)
- A repeat core biopsy on Cycle 1 Day 15 (\pm 3 days), preferably on the same tumor site if possible
- An optional final core biopsy after PD or off study, preferably on the same tumor site if possible

The first (pre-treatment) biopsy should be performed as soon as possible after consent is signed. For this reason, patients will be screened for accessibility of tumor tissue. Specifically, our radiologists will review the most recent images for each patient prior to enrollment. Only patients who, in their best estimation, have a tumor deposit(s), that are easily accessible by ultrasound or CT guidance in order to obtain serial core needle biopsies, will be eligible for study.

Patients will undergo core biopsies, as per standard protocol in the Department of Radiology. An 18-20 gauge needle will be used. At least three 1-2 cM core biopsies should be obtained with each biopsy. All samples should be labeled with the date, protocol number, protocol assigned patient number, and biopsy number (1 – pre-treatment; 2 – on-treatment; 3 – after PD or off study). The samples will be immediately placed in formalin and then embedded in paraffin.

Samples collected must be shipped at room temperature to [name] at:

Roswell Park Comprehensive Cancer Center
c/o [name]
[name]
[name]

Of note, patients who are on chronic anticoagulation will be required to hold anticoagulation prior to the biopsies being performed. Patients on warfarin must hold treatment for 5 days, but will be on low-molecular weight heparin (LMWH), 1mg/kg subcutaneously twice a day. The LMWH will continue until the last biopsy is complete. Patients may then resume warfarin the day after the last biopsy. Additionally, patients on LMWH will hold (*i.e.*, not receive) the dose of LMWH the morning of the procedure, but will resume the LMWH the evening of the day of the biopsy.

Throughout the study, the following labelling procedures will be followed

4.3.1.1 Patient Study Number Assignment

Patients will be de-identified and labelled with a 5 digit study label (X-XXX-X):

- The first number will be the site from which the patient was enrolled (single digit)
 - o 1 = Georgetown
 - o 2 = Additional Sites as Added
- The second number will be the site-assigned patient number (three digit)
- The third number will indicate the collection timing
 - o 1 = Pre-treatment
 - o 2 = On treatment

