3.1.3 Feasibility

Patients will be enrolled from the Lombardi Comprehensive Cancer Center (LCCC) at Georgetown University, and from partner institutions involved in this protocol. Only patients with mPAC will be eligible for enrollment. At our centers, over 300 new cases of pancreatic cancer are seen annually, at least one-half are metastatic, and around 25% of these patients would be eligible for further treatment after progression on 5-FU- and gemcitabine-based chemotherapy regimens. Therefore, around 18 patients would be eligible for enrollment in this trial each year. Based on this, we expect to accrue 1.5 patients per month, completing accrual in about 29 months.

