8.1.1.1 Patient Study Number Assignment

Patients will be de-identified and labeled with a 5 digit study label (X-XXX-X):

- The first number will be the site from which the patient was enrolled (single digit)
 - o 1 = Georgetown
- The second number will be the site-assigned patient number (three digit)
- The third number will indicate the collection timing
 - o 1 = Pre-treatment
 - o 2 = On treatment

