8.1.2 Assessment of Pharmacodynamic Effects of LEE011 and Everolimus

A formalin-fixed, paraffin embedded core sample from the pre-treatment and on-treatment tumor biopsies will be used to make slides to stain for the following markers by IHC with the indicated cutpoints:

- a. RB, defined as negative if tumor cells are devoid of nuclear staining, while lymphocytes and stromal cells have positive nuclear staining.
- b. pRB (phosphorylated Ser780), defined using a histoscore of intensity and percent of tumor cell nuclei staining.
- c. p16 levels are defined using established clinical staining criteria (0-3+)
- d. Cyclin D1, defined using intensity and predominant localization (nuclear/cytoplasmic)
- e. Ki67, defined as a percentage of positively stained nuclei in the tumor compartment
- f. MCM7, defined as a percentage of positively stained cells nuclei in the tumor compartment
- g. pS6 (Ser235/236) defined using a histoscore of intensity and percent of tumor cells staining

LEE011 directly suppresses the phosphorylation of RB which provides an assessment of on-target activity. Ki67 and MCM7 are markers of proliferation and are expected to diminish with treatment associated with response. RB, Cyclin D1, and p16 could be predictive markers of response, and the absence of RB and high-levels of p16 are associated with resistance. Phosphorylation of s6 protein is mediated by MTOR and provides a marker for the efficacy of MTOR inhibition by everolimus.

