9.5.2 Analytic plan for secondary objectives

9.5.2.1 Survival and response endpoints:

9.5.2.1.1 The nonparametric Kaplan-Meier method will be used to estimate median PFS.

9.5.2.1.2 The nonparametric Kaplan-Meier method will be used to estimate median OS.

9.5.2.1.3 We plan to determine the ORR within a $\pm 20\%$ range based on our sample size.

9.5.2.2 Adverse event data will be compiled and tabulated using descriptive statistics.

9.5.2.3 Pharmacodynamic analyses are exploratory, but we hypothesize that proliferation indices (Ki67 and MCM7) will be decreased in the on-treatment sample compared to the pre-treatment sample and could correlate with PFS. Similarly, expected decreases in levels of pRB, cyclin D1, p16, and increases in RB could correlate with PFS. Cox proportional hazard regression models will be fit to determine whether these secondary endpoints are associated with PFS.

9.5.2.4 NGS analysis is also exploratory in nature. Using results from these analyses will examine whether median PFS is different with patients with mutations in *CDKN2A* compared to those without these mutations.

9.5.2.5 ctDNA studies are exploratory and overall trends in serial measurements may support a response (or lack of response) signal to treatment and could be correlated with PFS as a surrogate marker of disease burden.

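### Tissue labels carry the time point and nothing requires masked IHC reading, so the pre/on-treatment comparison is open to reader bias; the site code, read literally, also allows duplicate labels

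*Combined protocol and SAP*

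**What the plan says.** **Labels.** Section 4.3.1.1 defines a label of the form X-XXX-X. On its last digit it says "The third number will indicate the collection timing", with 1 for pre-treatment and 2 for on treatment. Section 8.1.1.1 repeats the scheme. Section 4.3.1 adds: "All samples should be labeled with the date, protocol number, protocol assigned patient number, and biopsy number". It defines biopsy numbers 1 to 3, as does Section 8.1.1. Samples go to one outside centre.

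**Sites.** The first digit is 1 for Georgetown and "2 = Additional Sites as Added". The middle block comes from the site: "The second number will be the site-assigned patient number (three digit". Section 3.1.3 foresees enrolment at Georgetown "and from partner institutions involved in this protocol", in the plural.

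**Scoring.** Section 8.1.2 uses a histoscore for pRB, a 0-3+ grade for p16, and intensity with localization for cyclin D1. pS6 is "defined using a histoscore of intensity and percent of tumor cells staining". Ki67 and MCM7 are percentages of positive nuclei.

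**Expected direction.** Section 9.5.2 (item 9.5.2.3) says "we hypothesize that proliferation indices (Ki67 and MCM7) will be decreased in the on-treatment sample compared to the pre-treatment sample". It also expects pRB, cyclin D1 and p16 to fall and RB to rise. It gives no direction for pS6.

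**Status.** Section 8.1.1 calls this an important secondary endpoint and Section 9.4.2.5 lists it among the secondary endpoints. Sections 2.6 and 9.5.2.3 call it exploratory.

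**The concern.** The study has one arm, so each patient's pre-treatment sample is the only comparator for the on-treatment sample. A reader who knows which slide is which, and which way the result should go, can shift graded scores without intending to. Nothing in the design would reveal such a shift. Masking is the main protection available, and the plan does not mention it.

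The label also has to identify the patient, because the comparison is paired and the markers then enter Cox models for PFS. If two sites can issue the same label, one patient's on-treatment sample can be matched to another patient's pre-treatment sample, or a marker change to the wrong PFS time.

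At stake is the interpretability of data for which patients undergo two core biopsies.

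**Working it through.** The plan gives no sample size, alpha or test for the pre/on IHC comparison, so there is no stated figure to reproduce. The check is a comparison of texts with three illustrations.

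**1. Is the time point visible, and is it removed?** Timing can be read from the last label digit (4.3.1.1, 8.1.1.1), the biopsy number (4.3.1, 8.1.1) and the date (4.3.1). Section 8.1.2 says only that slides are made from the pre-treatment and on-treatment cores. Sections 4.3, 8 and 9 contain no recoding step, masked reading, random slide order or second reader.

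**2. Which markers combine graded scoring with an expected fall?**

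| Marker | Scoring in 8.1.2 | Definition in 9.4.2.5 | Direction in 9.5.2.3 |
|---|---|---|---|
| pRB | histoscore | positive/negative | fall |
| p16 | 0-3+ | positive/negative at 5% | fall |
| Cyclin D1 | intensity, localization | positive/negative | fall |
| Ki67, MCM7 | percentage | percentage, at least 3 randomly selected fields | fall |
| RB | negative if no nuclear staining | positive/negative | rise |
| pS6 | histoscore | histoscore | none stated |

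The argument is strongest for pRB, p16 and cyclin D1 as defined in 8.1.2.

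**3. Illustration: what would a scoring shift do?** Assume no true change and a constant reading shift of b, in SDs of the paired difference. A two-sided 5% paired t-test then has false-positive rate P(|T| > t(0.975, n−1)), where T is noncentral t with n−1 degrees of freedom and noncentrality b√n. For n = 26 and b = 0.2, the noncentrality is 0.2 × √26 = 1.02 and the rate is 0.165.

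| Pairs | b = 0 | b = 0.1 | b = 0.2 | b = 0.3 |
|---|---|---|---|---|
| 11 (stage 1) | 0.050 | 0.060 | 0.092 | 0.147 |
| 20 (assumed, some biopsies missing) | 0.050 | 0.071 | 0.136 | 0.247 |
| 26 (Phase II, all paired) | 0.050 | 0.078 | 0.165 | 0.313 |

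The values of b are assumptions. Twenty-six pairs is the Phase II ceiling: Section 4.3 waives unsafe biopsies, and Section 10.3 lets patients decline tissue collection.

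**4. Illustration: how many labels would coincide?** Read the scheme literally: first digit 2 at every added site, and each site numbering from 001. With two biopsies per patient, two added sites share 2 sites × 2 biopsies × (patients at the smaller site) non-unique samples. Site sizes are assumed.

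- 6 and 6 patients: 2 × 2 × 6 = 24 of 24 samples, on 12 distinct labels.
- 8 and 4 patients: 2 × 2 × 4 = 16 of 24.
- 10 and 3 patients: 2 × 2 × 3 = 12 of 26.

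**5. Illustration: what would mis-pairing do?** Swapping on-treatment samples between patients leaves the mean difference unchanged but widens its SD. With equal variances, within-pair correlation ρ and a fraction m mis-paired, the SD ratio is √[(1 − ρ(1 − m))/(1 − ρ)]. For ρ = 0.5 and m = 0.10 this is √(0.55/0.5) = 1.049; for m = 0.25 it is √(0.625/0.5) = 1.118. The loss is in precision and in the link between marker change and PFS, not in direction.

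**The case against.** **Unmasked reading is inferred.** A reader might conclude that the scorer is known to see the time point. No section says so. The label rules govern collected specimens, and a time point on the specimen is needed for custody and pairing. A laboratory manual, not among the documents, might cover masking. This stands: the defect is that the plan is silent on masking, not that the label carries timing.

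**The figures test an analysis that the plan does not name.** Section 9.4.2.5 plans a comparison and Section 9.5.2.3 names only Cox regression on PFS. A constant shift c in a change score leaves the Cox coefficient alone, because exp(β(x + c)) = exp(βc)·exp(βx) and the first factor goes into the baseline hazard. A t-test also does not suit the positive/negative definitions in 9.4.2.5. This stands too. The rates restate assumed shifts and are not estimates. The pre/on comparison itself remains exposed.

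**The collision needs a literal reading.** The first digit is meant to identify the enrolling site, so the added-sites line may be a placeholder for 2, 3 and so on. The date on the sample, central review of each patient before treatment (4.4.11.2) and the identification key held by the principal investigator (10.5) would help to catch errors. However, the date is not a patient identifier. Nor is the numbering rule settled elsewhere: 4.3.1 speaks of a protocol-assigned number, 8.1.1.1 codes only Georgetown, and 10.5 describes a letter and number.

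**Three further inferences fail.** A reader might infer that the optional third biopsy has no code; 4.3.1 and 8.1.1 give it biopsy number 3, and only the last-digit lists stop at 2. A reader might count field selection as reader judgement; 2.6.1 and 9.4.2.5 require randomly selected fields for Ki67 and MCM7. A reader might assume that every marker is expected to fall; RB is expected to rise and pS6 has no stated direction.

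**Conclusion.** The point holds in limited form. As written, the uncontrolled pre/on IHC comparison is open to reader bias: timing is on the specimen, no step masks the reader, and pRB, p16 and cyclin D1 combine graded scoring with an expected fall. The size is unknown. The range of 8% to 31% for 26 pairs depends entirely on assumed shifts of 0.1 to 0.3 SD and an assumed paired t-test.

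Separately, the site code permits duplicate labels if read literally and if at least two sites are added. The documents do not show that duplicates will occur.

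Neither issue touches the 8-week PFS decision or the choice of the recommended Phase II dose. The change is still worth making, because the comparison is a main reason for the two biopsies and the remedy costs almost nothing.

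**What to change.** **In Section 8.1.2:** the laboratory gives each slide a random code, with the key held by someone who does not score. A patient's pre- and on-treatment samples are stained in one batch. The reader stays masked to time point and outcome until scores are locked. If a laboratory manual already requires this, cite it here.

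**In Sections 4.3.1.1 and 8.1.1.1:** give each added site its own digit, or assign patient numbers centrally. Align the last-digit list with biopsy numbers 1 to 3, already defined in 4.3.1 and 8.1.1. Use the same numbering rule in 4.3.1 and 10.5.

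**Cost:** a few sentences and a code list. Same-batch staining delays the pre-treatment IHC read until after the Day 15 biopsy, and no decision in the plan depends on that read. Sample size, visits and treatment do not change. With masked reading the shift tied to time point is removed, and in the illustration the false-positive rate returns to 5%. With unique site codes or central numbering, duplicate labels fall to zero.
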